# **Patients and Methods**

## **Patients:**

This prospective study will be conducted in Anesthesia and ICU department in Minia University Hospital after obtaining approval from our faculty ethical committee and obtaining written informed consent from the patient's or the relatives in each case.

## **Methods**

### **Preoperative evaluation and ultrasonography:**

Preoperative evaluation and ultrasound examination will be performed by an anesthesiologists who will not be involved in laryngoscopy and intubation before the surgery, data was obtained in standard fashion. The patient's information, medical history, ) history of obstructive sleep apnoea (OSA) (diagnosed by polysomnography, or undiagnosed sleep apnoea suspected by the presence of snoring and cessation of breathing during sleep); Physical examination height, weight, body mass index (BMI), loose or protruding upper teeth, or partially missing upper incisors or canines;

### **Will evaluate the following variables:**

- 1- Mallampati score
- 2- Neck mobility (flexion/extension degrees from midline),
- 3- Upper lip bite test,
- 4- Temporomandibular joint mobility assessed by mouth-opening and forward movement of the jaw and the ability to protrude the lower teeth further than the upper teeth;
- 5- . A flexible ruler will be used to measure airway parameters, mouth opening (cm), thyromental distance (cm), sternomental distance

(cm), hyomental distance (cm) and neck circumference (cm) at the level of the thyroid cartilage.

The thicknesses of the anterior neck soft tissues will be measured with a portable ultrasound machine). A 6 to 13 MHz high frequency curvilinear ultrasound transducer was used for ultrasound scanning. Patients will be explained about the ultrasonography procedure and positioned in supine with the head in a neutral position. Ultrasonography with the probe placed in the transverse axis, craniocaudal sagittal scan, submental region of the neck. The distances will be measured at five levels (hyoid bone, epiglottis, cricothyroid membrane, thyroid isthmus and suprasternal notch) with normal and extended neck position in the median axis.

### **Intraoperative:**

After 5 min. preoxygenation, anesthesia will be induced with fentanyl (1-2  $\mu$ g/kg), propofol (2-4 mg/kg) and succinylcholine (1 mg/kg). with patient's head in sniffing position on a standard operating room pillow at a height of 5 cm., an anesthesiologist who is unaware of the ultrasound results will perform laryngoscopy with a Macintosh

No. 3 blade and insert an endotracheal tube of the proper size.

Laryngoscopic view will be graded according to the method described by Cormack and Lehane as grade 1 (full view of the glottis), grade 2 (glottis partly exposed, anterior commissure not seen), grade 3 (only epiglottis seen), or grade 4 (epiglottis not seen). No external laryngeal pressure will be applied while reporting the laryngeal view.

If intubation failed after three attempts, the study ended and alternative methods for airway placement will be pursued.

To confirm endotracheal intubation, tracheal ultrasound during endotracheal intubation (ETI) will be performed. Ultrasound probe will be set on the outside of larynx and glottis during intubation and tube passage through trachea is checked.

Statistical analysis; Our results will be statistically analyzed and expressed as tables and figures.

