# Introduction

Proper airway management (AM) is an essential goal for anesthesia providers. Poor airway assessment and planning contributed to unfortunate airway outcomes. Airway management skills are indispensable for an emergency physician. Unrecognized airway accidents such as esophageal intubation tend to occur more in emergency settings  where it is reported as 6%-16%.

The inability to successfully intubate a pharmacologically paralyzed patient can be a disastrous situation. Although patients who are potentially difficult to intubate can often be predicted clinically, this method does not provide complete assurance, providing a requirement to consider other methods.  Also, confirmation of proper tracheal intubation could be performed primarily by direct laryngoscopy, auscultation of Gurgling sounds in the epigastric region, lung auscultation, observation of water vapor on endotracheal tube wall, using esophageal detector device, CXR and ETCO2 (end-tidal CO2 pressure) that each of the above-mentioned methods have its own limitations .

Obesity is a well-known independent predictor of difficult intubation, but increased body mass index poorly predicts difficult laryngoscopy.

A large neck circumference is among the suggested predictors of difficult intubation, especially in obese patients and it has been reported to predict difficult laryngoscopy. Neck circumference, though, does not indicate the amount of soft tissue at various topographic regions within the neck. Distribution of fat in different neck areas may provide better information than neck circumference. 

Ultrasound (US) offers a number of attractive advantages compared with competitive imaging techniques or endoscopy for imaging critically ill patients. It is widely available, portable, repeatable, relatively inexpensive, pain-free, and safe.

Although the earliest reports dealing with US applications in clinical medicine include the description of soft-tissue imaging of the pretracheal structures and anterior Ultrasound (US) evaluation of the airway is found to be an excellent tool in different medical settings including the operating room, intensive care unit and in the emergency department (ER). The utility of the US in the airway management is not limited to the upper airway assessment; it has been also used to evaluate the lower airway, lungs and pleura .

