## **Aim of the work**

The aim of the study is to determine whether preoperative ultrasound assessment of the upper airway can predict difficult laryngoscopy in emergency surgical obese patients , by analysis correlations between ultrasound measurements of anterior cervical soft in the upper airway, and the Cormack–Lehane grade. And evaluate its role in confirming the endotracheal placement

The secondary objective was to determine whether clinical screening tests are independent predictors of difficult airway.

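### Does ending the study after three failed intubation attempts drop the patients who matter most to the outcome?

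*Protocol*

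**What the plan says.** The Aim of the work is to "determine whether preoperative ultrasound assessment of the upper airway can predict difficult laryngoscopy in emergency surgical obese patients", by correlating ultrasound soft-tissue measurements with the Cormack-Lehane grade. A second part of the aim follows: "And evaluate its role in confirming the endotracheal placement".

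The data arise in this order:

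- **Predictors.** "Preoperative evaluation and ultrasound examination will be performed by an anesthesiologists who will not be involved in laryngoscopy". They are recorded before surgery.
- **Outcome.** "Laryngoscopic view will be graded according to the method described by Cormack and Lehane as grade 1 (full view of the glottis", and so on to grade 4. The grade describes the view at laryngoscopy.
- **Tube confirmation.** "tracheal ultrasound during endotracheal intubation (ETI) will be performed".
- **Stopping rule.** "If intubation failed after three attempts, the study ended and alternative methods for airway placement will be pursued".

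The protocol does not say what happens to a patient's data once the stopping rule applies. Its analysis text is a single general sentence that defines no analysis population.

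**The concern.** For one patient, a statement that the study ended can mean that study procedures stop or that the patient leaves the study. No sentence elsewhere in the protocol chooses between the two.

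The second reading would matter because the loss would not be random. Three failed attempts are plausibly tied to a poor view, so withdrawal would depend on something close to the outcome. The observed share of difficult laryngoscopies would fall if failures are mostly grade 3 or 4. The apparent accuracy of ultrasound would shift in a direction that depends on whether ultrasound had flagged those patients.

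The loss would also be needless, since the data for the main aim can be complete by then. For tube confirmation, only misplaced tubes can show that ultrasound detects misplacement, and failing patients are one plausible source of them.

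**Working it through.** **1. Reading the sentence.** The stopping rule is joined to the pursuit of other airway methods, which is the language of halting a procedure so that rescue can follow. Where the protocol means removal, under Exclusion criteria, it says outright that patients are excluded. The stopping rule uses no such word and mentions neither withdrawal, deletion nor replacement.

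**2. What exists when the rule applies.** Clinical tests and ultrasound measurements were taken before surgery. The Cormack-Lehane grade needs a view, not a tube, and three attempts have been made. Followed as written, the protocol therefore has predictor and outcome for a failed patient. If they are kept, the rule causes no bias in the main aim.

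**3. Size if the patient were withdrawn.** The protocol gives no failure rate, prevalence or effect size, so every input here is an assumption:

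- prevalence of difficult laryngoscopy p = 0.20;
- all failures occur among difficult patients, a share f of them;
- thickness has unit SD, shifted by 0.8 SD in difficult patients who are intubated and by s = 0 to 1.5 SD in those who fail.

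Formulas:

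- failures among all patients = p·f
- prevalence after withdrawal = p(1−f)/(1−pf)
- AUC after withdrawal = Φ(0.8/√2) = 0.714
- AUC with everyone kept = (1−f)·0.714 + f·Φ(s/√2)
- error = value after withdrawal minus value with everyone kept

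| f | Failures, all patients | Prevalence after withdrawal | AUC, all kept (s=0 to s=1.5) | AUC error | Correlation, all kept (s=0 to s=1.5) | Correlation after withdrawal |
|---|---|---|---|---|---|---|
| 0.02 | 0.4% | 19.7% | 0.710 to 0.717 | +0.004 to −0.003 | 0.299 to 0.309 | 0.303 |
| 0.10 | 2% | 18.4% | 0.693 to 0.728 | +0.021 to −0.014 | 0.275 to 0.327 | 0.296 |
| 0.25 | 5% | 15.8% | 0.661 to 0.750 | +0.054 to −0.035 | 0.231 to 0.360 | 0.280 |

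The correlation is between thickness and grade 3–4 as yes/no. The AUC error is zero when failures have the same shift as other difficult patients (s = 0.8).

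**4. A second model.** A simulation of 1,000,000 patients assumed about 20% grade 3–4 and an ultrasound–difficulty correlation of 0.3 or 0.5. Failures of 1% to 5% of all patients were drawn from the upper tail of a score correlated 0.8 with difficulty. With correlation 0.3, dropping them lowered Spearman's coefficient from 0.259 to between 0.253 and 0.239. With correlation 0.5 it fell from 0.434 to between 0.426 and 0.406. The AUC fell by at most 0.011 (0.748 to 0.737). Counts moved more: 5% to 22% of grade 3–4 patients and 25% to 65% of grade 4 patients were lost.

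**5. Tube confirmation.** The Introduction cites esophageal intubation in 6% to 16% of emergency cases, or 6 to 16 per 100 intubations. Suppose half, 3 to 8, fell in patients who then failed three attempts. Each failing patient contributes three failed attempts, so per 100 patients the scenarios in step 3 give:

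- 0.4 × 3 = 1.2 failed attempts
- 2 × 3 = 6 failed attempts
- 5 × 3 = 15 failed attempts

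Losing 3 to 8 misplaced tubes is impossible in the first scenario. In the second, 8 is impossible. In the third, 8 needs 8/15 = 53% of all failing attempts to be misplaced. A large loss on this part of the aim therefore does not fit the failure rates assumed for the main aim. Failed first or second attempts in patients later intubated would remain in any case.

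**The case for a change.** The strongest contrary argument is that the sentence instructs the people collecting data. If they took it as withdrawal and stopped recording, no later analysis plan could recover the loss, and one added sentence would prevent it. The loss would be related to the outcome and, in the simulation, would take up to 65% of grade 4 patients.

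Part of this stands. The wording is ambiguous, the selectivity is plausible, and stating the retention rule would cost almost nothing. But the predictors are on file before laryngoscopy and the grade belongs to the laryngoscopy itself, so little depends on recording after the rule applies. The depletion of grade 4 hardly moves the correlation and AUC, which bear most directly on the main aim. The share of difficult laryngoscopies moves more, but estimating it is not a stated aim.

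The tracheal scan is more exposed, because a reading not noted during a failed attempt is gone. Yet it is planned during intubation, and the rule acts only after the third failure.

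**Conclusion.** No change to the plan follows. The protocol contains no withdrawal rule. It has a rule for ending study procedures and is silent about data already recorded. Keeping those data is the natural course, and defining who is analysed is commonly left to a statistical analysis plan, which is not at hand here. With the data kept, the bias in the main aim from this rule is nil.

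If the rule were nevertheless applied as withdrawal, the illustrations put the AUC error at no more than about 0.02 in either direction when up to 2% of all patients fail. It reaches −0.035 to +0.054 only when a quarter of difficult patients fail and their thickness lies at the extremes assumed. These figures rest on 20% prevalence, a 0.8 SD shift and all failures being difficult laryngoscopies, none of which the protocol states. Some failures may in fact have a grade 1 or 2 view.

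No figure is offered for lost precision in tube confirmation, because it would need more misplaced tubes among failing patients than the lower failure rates allow.

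### Confirming tube placement by ultrasound is part of the aim, but the protocol designates and records no reference for where the tube went

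*Protocol*

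**What the plan says.** The Aim of the work section first sets out the prediction of difficult laryngoscopy, then adds a second task for ultrasound: "And evaluate its role in confirming the endotracheal placement". It names no measure of performance for that task.

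The Intraoperative section carries it out with one procedure: "To confirm endotracheal intubation, tracheal ultrasound during endotracheal intubation (ETI) will be performed". The reading is described only as follows: "Ultrasound probe will be set on the outside of larynx and glottis during intubation and tube passage through trachea is checked".

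The Introduction names several conventional methods, beginning with the statement that "confirmation of proper tracheal intubation could be performed primarily by direct laryngoscopy". It goes on to auscultation, tube condensation, an esophageal detector device, chest X-ray and ETCO2, and says that each has limitations. These are background; none is assigned as a study measurement.

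**The concern.** The prediction aim has a named outcome, the Cormack-Lehane grade, assessed by someone blinded to ultrasound results. The confirmation aim has no counterpart: the test being evaluated also supplies the only tube-position result that the protocol specifies.

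The Introduction motivates the work partly by unrecognized esophageal intubation, so a reader will expect the study to say whether ultrasound picks up a misplaced tube. A high percentage read as tracheal could come from skilled intubation, from a good test, or from a test that calls nearly every tube tracheal. Presented alone, it invites a claim about detection that it can neither support nor refute.

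**Working it through.** **Step 1. Look for a reference in the protocol.** Five items might be taken for one.

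- *Background list (Introduction).* It names methods but assigns none to the study.
- *Laryngoscopy (Intraoperative).* It is performed in every patient and is a listed confirmation method. The result taken from it is the view: "Laryngoscopic view will be graded according to the method described by Cormack and Lehane". The grade describes how much of the glottis is seen, not where the tube went.
- *Three-attempt rule.* "If intubation failed after three attempts, the study ended and alternative methods for airway placement will be pursued". Someone must judge failure, but who does so, and by what method, is not stated.
- *Blinded laryngoscopist.* "an anesthesiologist who is unaware of the ultrasound results will perform laryngoscopy with a Macintosh". The preoperative section says that "ultrasound examination will be performed by an anesthesiologists who will not be involved in laryngoscopy and intubation before the surgery", so the blinding most likely concerns the preoperative scan. Even if it also covered the tube scan, no verdict on tube position by this person is specified.
- *The tube scan itself.* This is the test under evaluation.

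No item is a designated and recorded reference.

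**Step 2. What the ultrasound reading alone can show.** The protocol gives no figure to reproduce. Let π be the true share of tracheal tubes, Se the share of tracheal tubes read as tracheal, Sp the share of misplaced tubes read as not tracheal, and q the observed share read as tracheal. Then

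q = Se·π + (1 − Sp)·(1 − π).

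One observed quantity has to serve for three unknowns. Solving for one of them, Se = [q − (1 − Sp)(1 − π)]/π. Two limits apply:

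- A test no worse than chance has Se ≥ 1 − Sp, which reduces to Sp ≥ 1 − q.
- Se ≤ 1 gives Sp ≤ 1 − (q − π)/(1 − π) when q > π; otherwise the upper limit is 1.

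**Step 3. Illustration.** The Introduction quotes 6%-16% for emergency settings. It is background, not a design input, and is used here as an assumption; the values of q are hypothetical. With 6% misplaced (π = 0.94) and q = 0.94, the lower limit is Sp = 1 − 0.94 = 0.06 and the upper limit is 1.00. Per 100 placements:

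| Sp | Se | Tracheal, read as tracheal | Misplaced, read as tracheal | Total read as tracheal |
|---|---|---|---|---|
| 1.00 | 94/94 = 1.000 | 94 | 0 | 94 |
| 0.50 | 91/94 = 0.968 | 91 | 3 | 94 |
| 0.06 | 88.4/94 = 0.940 | 88.4 | 5.6 | 94 |

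The three rows give the same observed result. With 16% misplaced (π = 0.84) and the same q = 0.94, the upper limit becomes 1 − 0.10/0.16 = 0.375, so Sp runs from 0.06 to 0.375. The range therefore also shifts with a misplacement rate that the study would not observe. No sample size enters: more patients estimate q more precisely but do not separate the rows.

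**The case against.** The strongest reply is that the protocol never promises an accuracy study. It names no sensitivity or specificity, and the aim can be read as a descriptive report of how often tracheal passage is seen. On that reading, aim and procedure agree. This stands, and it is why a change of wording is an acceptable repair.

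Two stronger readings are tempting and are not supported:

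- *Ultrasound is the only check of tube position that will take place.* Laryngoscopy is performed in every patient, and the attempt rule presupposes some judgement of each attempt. Silence does not show that nothing else is noted in practice. The gap is that nothing else is designated or recorded under the protocol.
- *No analysis plan could ever repair this.* If the site routinely records another confirmation result, an analysis plan could designate it as the reference. The protocol does not commit to recording one, and a bedside result that was never recorded cannot be supplied later.

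It is also fair to say that the numbers illustrate a general identity and are not evidence about this trial. The 6%-16% may not suit a population that excludes patients with a full stomach and unstable patients. Sensitivity is much less affected: in the 6% case it lies between 0.94 and 1.00. Finally, a reference does not guarantee a useful estimate of specificity. At an assumed 1% misplaced, there would be about one such tube per 100 placements.

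**Conclusion.** The point holds in a limited form. The protocol specifies a single observation of tube position, made by the test being evaluated, and designates no reference. Following it exactly yields the proportion of placements with tracheal passage seen. It does not yield the ability of ultrasound to detect misplaced tubes, which is not identifiable from that proportion at any sample size. Under the illustrative 6% misplaced and 94% read as tracheal, specificity from 0.06 to 1.00 fits equally well, assuming only that the test is no worse than chance.

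How much this matters depends on what the aim means. If it means detection of misplacement, this part of the aim cannot be answered as written. If it means description, only the wording needs to change. The point should be settled before data are collected. The prediction of Cormack-Lehane grade is untouched.

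**What to change.** In the Intraoperative section, designate one confirmation method that the Introduction lists and the site already uses as the reference for tube position. State that it serves the analysis only and is not a rule for care. Record its result and the ultrasound reading for each attempt, noting the ultrasound reading first where existing staffing allows. Report agreement together with the number of misplaced tubes observed. Acknowledge that the reference is imperfect, and limit any statement about detection to what that number supports.

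If no reference can be recorded, restate this part of the Aim of the work as descriptive: the proportion of placements in which tracheal passage was seen, with no claim about detecting misplacement.

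The first option costs one or two form fields per attempt, assuming the method is already in routine use, which the protocol does not say. The estimate may be imprecise if misplacements are few. The second option costs one sentence and gives up the detection question.

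### Does placing an ultrasound probe on the larynx during intubation compromise the Cormack–Lehane grade used for the main aim?

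*Protocol*

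**What the plan says.** The Aim of the work section sets out to predict difficult laryngoscopy "by analysis correlations between ultrasound measurements of anterior cervical soft in the upper airway, and the Cormack–Lehane grade". The grade is therefore the reference measure for the main aim. The same section adds a second use of ultrasound: "And evaluate its role in confirming the endotracheal placement".

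The preoperative scan and the laryngoscopy are done by different people. On the scan: "Preoperative evaluation and ultrasound examination will be performed by an anesthesiologists who will not be involved in laryngoscopy and intubation before the surgery". On the laryngoscopy: "an anesthesiologist who is unaware of the ultrasound results will perform laryngoscopy with a Macintosh" blade.

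The Intraoperative section puts one condition on the grading: "No external laryngeal pressure will be applied while reporting the laryngeal view". After the rule on failed attempts it turns to tube confirmation, where "tracheal ultrasound during endotracheal intubation (ETI) will be performed", and it describes the technique: "Ultrasound probe will be set on the outside of larynx and glottis during intubation and tube passage through trachea is checked".

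No sentence says whether the probe is on the neck when the grade is given.

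**The concern.** To show the tube passing, the probe has to be in position by the time the tube arrives. The grade comes from the same laryngoscopy, probably moments before. The protocol asks for a view free of outside pressure, and it also asks for an object to be placed on the larynx at about the same time.

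If some grades were given with a probe pressing on the larynx and others without, the grade would not mean the same thing in every patient. The correlation with soft-tissue thickness would then be measured against an inconsistent reference, and the share of patients counted as difficult could shift. The protocol names no data item for probe position at grading, so nothing in it shows that affected grades could be identified afterwards.

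A lesser worry is masking, because a live scan might be visible to the laryngoscopist. The results that the laryngoscopist must not know are most naturally the preoperative measurements, so this matters only if the screen can be seen before the grade is given.

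**Working it through.** The protocol states no figure on this point, so there is nothing to reproduce. The check is first a reading of the text and then an illustration of size.

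**Can both instructions be obeyed?**

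1. The ban applies while the view is being reported. It names neither a hand nor any other source of pressure.
2. The probe instruction gives a site (outside of the larynx and glottis), a period (during intubation) and a task (checking tube passage). It does not say that the probe presses, or that it is in place when the laryngoscope goes in.
3. Three sequences are possible:
   - Grade given, then probe placed: both instructions are met.
   - Probe resting without pressure, then grade given: both are met.
   - Probe pressing while the grade is given: the ban is broken.
4. The harmful sequence is therefore a departure from the protocol. A team that follows the text records a grade free of outside pressure.

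**How much could departures matter?** All inputs here are assumed; none comes from the protocol.

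- True grade *G* is scored 1–4 with shares 0.40, 0.40, 0.15 and 0.05.
- A share *s* of patients is recorded one grade off, capped at 1 and 4.
- The error is unrelated to the ultrasound measurement given the true grade, and mean thickness is linear in grade.

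Under these assumptions, corr(ultrasound, recorded grade) = corr(ultrasound, *G*) × corr(*G*, recorded grade).

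Moments of *G*: mean = 0.40 + 0.80 + 0.45 + 0.20 = 1.85. Mean square = 0.40 + 1.60 + 1.35 + 0.80 = 4.15. Variance = 4.15 − 1.85² = 0.7275.

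*Recorded one grade worse.* Only grades 1–3 (95%) can move, and the covariance of *G* with being able to move is −0.05 × (4 − 1.85) = −0.1075.

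- Covariance of true and recorded grade = 0.7275 − 0.1075*s*
- Variance of recorded grade = 0.7275 − 0.215*s* + 0.95*s*(1 − 0.95*s*)
- At *s* = 0.10: 0.71675 / √(0.7275 × 0.79198) = 0.944
- At *s* = 0.30: 0.69525 / √(0.7275 × 0.86678) = 0.876

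*Recorded one grade better.* Only grades 2–4 (60%) can move, and the corresponding covariance is 0.40 × (1.85 − 1) = 0.34.

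- Covariance of true and recorded grade = 0.7275 − 0.34*s*
- Variance of recorded grade = 0.7275 − 0.68*s* + 0.6*s*(1 − 0.6*s*)
- At *s* = 0.10: 0.6935 / √(0.7275 × 0.7159) = 0.961
- At *s* = 0.30: 0.6255 / √(0.7275 × 0.6711) = 0.895

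| Share moved | Multiplier, worse | Multiplier, better | True *r* = 0.50 becomes |
|---|---|---|---|
| 0% | 1.000 | 1.000 | 0.50 |
| 10% | 0.944 | 0.961 | 0.472 or 0.480 |
| 30% | 0.876 | 0.895 | 0.438 or 0.448 |

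The share at grade 3 or 4 starts at 0.15 + 0.05 = 20%. With 10% moved it becomes 20% + 0.10 × 40% = 24% (worse) or 20% − 0.10 × 15% = 18.5% (better).

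These results show what a given error rate would do. They are no evidence that the probe causes any error.

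**The case for a change.** The best case for a change has four parts.

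- **Paragraph order does not give the sequence.** The probe is described after the rule on failed attempts, yet it is used during intubation. This stands, and the conclusion here does not rely on paragraph order.
- **A reader may take the ban to mean a hand manoeuvre only.** That reading is possible. But the wording is not so limited, and its evident purpose is an unaided view. An anesthesiologist who respects that purpose has no reason to exempt a probe. Practice may vary between operators, but the study runs in one department of one hospital (Patients section), so differing habits between sites do not arise.
- **Analysis could not repair it.** The protocol mentions no record of probe position. Neither the case report form nor an analysis plan is at hand, so it cannot be said that no record will exist.
- **The error might not be random.** If probe force rose with neck thickness, the error would be related to the predictor and could bias the correlation in either direction, so the attenuation figures would not apply. This is a fair limit on the illustration, but it adds a further assumption to an effect that the protocol does not show.

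Against a firm sequencing rule there is also a cost. Little time separates the grade from the tube, so holding the probe back may lose the start of tube passage and weaken the check on tube placement.

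**Conclusion.** The concern describes the text correctly but does not call for a change. The protocol leaves out the order of two bedside steps. It does not contain a rule that produces a wrong grade, because its ban on outside pressure already rules out the harmful sequence. What remains is a risk of non-adherence, which the team can manage by calling the grade before the probe is applied or by resting the probe without pressure. A line saying that the ban includes the probe would do no harm, but it is optional.

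The size of any effect cannot be derived from the protocol and may be nil. On the assumed grade mix, with error unrelated to the ultrasound measurement, one patient in ten misgraded by a full step lowers a correlation by about 4% to 6%, and three in ten by about 10% to 12%. The conclusion rests on reading the ban as covering pressure from any source, which is what its words say.
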